# mCRPC patients (Part 1 and Part 2 Arms 1A and 1B)

Bone scintigraphy (bone scans) and CT/MRI chest, abdomen, and pelvis should be performed at the following time points:

- During the screening period (within 28 days before C1D1 [baseline])
- At C3D15 (± 7 days)
- Then every 8 weeks (±7 days) for 24 weeks, i.e., between C6D1 and C8D15
- And every 3 months (±7 days) thereafter, i.e., from C11D15 until disease progression is assessed by the investigator or the start of new anti-cancer therapy or withdrawal of consent, or death, whichever occurs first
- At EoT visit (only if clinically indicated); not required if previous imaging was performed within ≤9 weeks before the EoT visit

Patients in Arm 1B who move to treatment with cemiplimab monotherapy following progression after BNT112 monotherapy, should have radiographic assessments performed every 3 months ( $\pm 7$  days) thereafter, until disease progression is assessed by the investigator or the start of new anti-cancer therapy or withdrawal of consent, or death, whichever occurs first.

CONFIDENTIAL Page 73 of 122

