#### 2. MEASURES OF RESPONSE:

The PCWG3 criteria for disease response in a patient are considered met if 1 or more of the following conditions occur:

- a) PSA response:
- PR: \ge 50\% decline in PSA from baseline confirmed at least 4 weeks later
- SD: Serial PSA measurements that do not meet the criteria for PR or PD
- b) Radiological response:
- Soft tissue/visceral disease:
  - CR: Disappearance of all target lesions. A reduction in short axis to <10 mm must be seen in any pathological lymph nodes. No new lesions.
  - PR: 30% decrease in the sum of the longest diameter of target lesions.
  - SD: No evidence of PD, CR or PR.
- Bone disease response
  - Bone scan is not used as part of the response criteria. Bone scans will be evaluated for progression only.
- c) Circulating tumor cell (CTC) response:
- Conversion of CTC  $\geq 5/7.5$  mL to  $\leq 5/7.5$  mL at 9 weeks. If there is a CTC response, this must be confirmed by an additional  $\leq 5/7.5$  mL result at least 4 weeks later.

CONFIDENTIAL Page 114 of 122

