	
LPC patients will be treated with up to 8 cycles or until unacceptable toxicity or disease progression. One cycle is defined as 21 days. EoT assessment will be performed up to 21 days after administration of last dose of IMP for patients who discontinued trial treatment, except if patient was lost to follow-up or died.
 
After EoT assessment a Safety follow-up (FU) after 30 days for Arm 2 and Arm 3 and an additional Safety FU after 90 days for Arm 2 patients are performed. Both Arms 2 and 3 will be followed up 6 and 12 months after last IMP administration for efficacy.
 
Trial duration:
 
First patient was included on 19 December 2019.
 
The end of the trial is defined as the date of last patient contact, whether in-person or by phone, for the last patient in the trial globally, including the efficacy follow-up for 12 months after the last dose of trial treatment.

Planned number of patients	
There will be 3 to 9 patients in Part 1 (dose titration part, single arm) and up to 106 patients in Part 2 (expansion part, 4 arms: up to 33 patients in Arm 1A and Arm 1B, respectively, and approximately 20 patients in Arm 2 and Arm 3, respectively). Drop-outs may be replaced. In total, there will be approximately 115 patients.
 
Re-screening of patients is allowed.

Randomization and blinding	
At screening, patients will be assigned a unique number (patient identification code), regardless of whether they actually receive trial treatment.
 
In Part 2, patients with mCRPC treated in Arm 1A or Arm 1B, and patients with LPC treated in Arm 2 or Arm 3, will be randomized in 1:1 ratio. Central randomization will be used. No stratification factors will be used for the randomization.
 
The site will contact the central randomization service prior to the start of trial treatment administration for each patient. The treatment assignment will be recorded on the applicable electronic case report form (eCRF), as required. This is an open-label trial.

Tumor assessment schedule	
Part 1 and Part 2 Arms 1A and 1B (mCRPC):
 
Bone scintigraphy (bone scans) and CT/MRI of the chest, abdomen, and pelvis should be performed at the following time points:
 
 - during screening period (within 28 days before C1D1) - at C3D15 (±7 days)

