The rules for the definition of BOR based on PCWG3 are referring to the following data reported in the CRF:

- Confirmed PSA response reported by the investigator (see Section 8.2 for more details regarding PSA response confirmation)
- Radiological Soft Tissue Evaluation (response data collected in the CRF on the “RECIST 1.1” page)
- Clinical Progression (data collected in the CRF on the “Clinical Progression” page)
- Bone Disease Progression (data collected in the CRF on the “Bone Lesion” pages with Clinical Impression = Progression)

Only assessments after first administration of IMP and prior to or at the start date of the first subsequent anti-cancer therapy will be considered in the derivation. Overall response of PD within 14 days after start date of the first subsequent anti-cancer therapy will be considered.

Only responses up to and including the date of the first progressive disease will be considered in the derivation of the BOR.

Overall Response of CR, PR, SD per PCWG3 is based on radiological soft tissue response or confirmed PSA response.

Progression of Disease per PCWG3 is based on the earliest radiological soft tissue progression, Bone disease progression, confirmed PSA progression or clinical progression.

The following order of tumor response categories will be used, with “Complete Response” is the best category:

Complete Response (CR) – Partial Response (PR) – Stable Disease (SD) – Progressive Disease (PD) – Not Evaluable (NE) – Not Applicable (NA).

Derivation of PSADT:

PSADT will be derived based on the PSA measurements provided by the investigator in the database and collected during the trial at screening visit and during each cycle.

PSADT will be calculated post-treatment on C4D1 and D1 of every fourth subsequent cycle (e.g. C8D1, C12D1, etc.) in Part 1 and Part 2 Arms 1A and 1B, or on C4D1, C8D1, and EoT in Part 2 Arms 2 and 3.

PSA measurements reported after EoT visit or after start of the first subsequent anti-cancer therapy will not be considered in the derivation of PSADT.

PSADT will be calculated using a linear regression model of the natural logarithm of PSA values and time ([3] and [<https://drhaddad.com.au/wp-content/uploads/2022/07/13.pdf>], [8]).

Derivation of PSADT post-treatment at every fourth subsequent cycle:

1. Compute the slope of the regression line of natural logarithm of PSA vs. time (which is the number of doublings per unit time) where PSA is the PSA level in ng/mL at each time point

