8.7 Efficacy analyses

8.7.1 Primary analysis

8.7.1.1 Primary Efficacy Endpoint

Objective Response Rate

For Part 2, Arms 1A and 1B, ORR is defined as primary efficacy endpoint. The primary analysis will be performed using the mITT set.

The ORR is defined as the number of patients with CR or PR as best objective response per PCWG3 divided by the number of patients in the mITT set. Patients not meeting the criteria for CR or PR, including those without any post-baseline response assessments, will be considered as non-responders. The ORR will be summarized with absolute and relative frequencies along with two-sided 95% Clopper-Pearson CIs by treatment group.

For each Part 2 Arm 1A and 1B the null hypothesis (see Section 4) that the true response rate is 5% will be tested against a one-sided alternative (i.e. H_0 : ORR=5% versus H_1 : ORR >5%). There will be no formal comparison between treatment groups.

BOR (all categories) based on PCWG3 will be summarized with absolute and relative frequencies.

Further, the BOR (all categories) based on Radiological Soft Tissue Evaluation will be summarized with absolute and relative frequencies.

For Part 1, ORR is defined as secondary endpoint as best objective response and will be analyzed descriptively.

Tumor response assessment including overall response, BOR and clinical progression as documented in the eCRF will be listed. In addition, listings including all tumor assessments per PCWG3 (target lesion, non-target lesion, new lesion) will be generated.

Subgroup analyses of the primary efficacy endpoint will be performed for the mITT set.

Sensitivity analysis

For the primary endpoint ORR, sensitivity analyses will be performed using the ITT set and the PP set.

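### PCWG3 best overall response gives progression no precedence on a shared date, so a first CR or PR dated on the day of bone or clinical progression counts in the primary ORR

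*SAP*

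**What the plan says.** SAP 8.2 (Key definitions, BOR based on PCWG3) sets four rules.

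- Source of response: "Overall Response of CR, PR, SD per PCWG3 is based on radiological soft tissue response or confirmed PSA response".
- Source of progression: "Progression of Disease per PCWG3 is based on the earliest radiological soft tissue progression, Bone disease progression, confirmed PSA progression or clinical progression". Bone and clinical progression sit on their own CRF pages, apart from the soft-tissue page.
- Date limit: "Only responses up to and including the date of the first progressive disease will be considered in the derivation of the BOR".
- Choice of category: the best one wins, in the order CR, PR, SD, PD, NE, NA.

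SAP 8.7.1.1 carries the result into the primary endpoint: "The ORR is defined as the number of patients with CR or PR as best objective response per PCWG3", over the mITT set.

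Protocol Appendix 9 treats response as met when one or more conditions hold, and progression likewise. On bone it says: "Bone scan is not used as part of the response criteria. Bone scans will be evaluated for progression only". Protocol 8.1.1.1 and SAP 3.2 place bone scans and CT/MRI at the same time points, with a window of ±7 days.

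**The concern.** With a single source of response, an inclusive date limit is harmless. Each assessment has one result, and the PD date must be included so that PD can itself be the BOR. The same sentence appears in the soft-tissue BOR definition and does no damage there.

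With four sources it also admits a better result from the very assessment that shows progression, and the ranking then prefers that result. A patient whose only response-level CT coincides with progression elsewhere is counted as a responder, although by the SAP's own definition of PD he has progressed on that date.

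The numerator of the primary ORR is at stake. The planned ITT and PP sensitivity analyses would not reveal the problem, because they change the set of patients and not the BOR derivation.

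**Working it through.** **The plan's own figures.** SAP 6 gives 20 evaluable patients in stage 1 (may stop at 1 or fewer responses), rejection at 5 or more of 33, type I error 2.5% and power 80% at a true rate of 20%. The exact rejection probability is the sum over x1 = 2 to 20 of Bin(20, x1, p) × P(X2 ≥ 5 − x1 given 13 patients). It is 0.0218 at p = 0.05 and 0.802 at p = 0.20. Power reproduces, and 2.5% is a ceiling on the type I error. The denominators 20 and 33 used below come from this design.

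**Dates.** C3D15, the first on-treatment scan, is day 1 + 2 × 21 + 14 = 57.

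**The rule applied to patient records.** Let D be the earliest PD date from any component. Keep every component response dated on or before D and take the best. The alternative keeps CR, PR or SD only if dated before D, with PD on D.

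| Records | SAP as written | PD takes precedence |
|---|---|---|
| Soft-tissue PR day 57, bone PD day 57 | PR | PD |
| Soft-tissue PR day 57, clinical PD day 57 | PR | PD |
| Soft-tissue SD day 57, bone PD day 57 | SD | PD |
| Clinical PD day 50, soft-tissue PR day 57 | PD | PD |
| Soft-tissue PR day 57, bone PD day 113 | PR | PR |

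Only shared dates differ. A response before progression is a legitimate BOR, and one after it is already excluded.

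**Scan order within one window.** Take the bone PD date as the date of the scan that first shows it. CT with PR on day 57 and bone scan with PD on day 59 gives PR. Bone scan on day 57 and CT on day 59 gives PD. Both pairs lie within ±7 days of one scheduled assessment, so the order of two appointments decides the outcome.

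**Confirmation.** The confirmation rules in SAP 8.2 cover PSA responses only. One soft-tissue PR on the PD date is therefore enough for BOR. For PSA the SAP already applies the missing principle: bone or clinical progression between a PSA PR and its confirming result blocks the confirmation.

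**Size.** ORR = responders / n, so one patient adds 1/33 = 3.0 points or 1/20 = 5.0 points. With two-sided 95% Clopper-Pearson limits:

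| Responders | ORR | 95% CI |
|---|---|---|
| 1 of 20 | 5.0% | 0.1 to 24.9 |
| 2 of 20 | 10.0% | 1.2 to 31.7 |
| 4 of 33 | 12.1% | 3.4 to 28.2 |
| 5 of 33 | 15.2% | 5.1 to 31.9 |

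**The case against.** The strongest reply is that a PCWG3 overall response is clearly intended. SAP 8.2 speaks of an overall response as distinct from BOR, and Listing 16.2.6.1.7 is planned to show it. A programmer might apply the usual convention that any PD makes the assessment PD. This stands only in part: the level is named, but no derivation is given for it, and the rule that is written yields PR.

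The bone examples are also conditional. Appendix 9 requires new lesions at C3D15 to be confirmed by a scan at least 6 weeks later. The SAP takes bone progression from the investigator's entry and does not say which scan supplies the date. If the confirmatory scan does, bone PD falls no earlier than day 57 + 42 = 99, and a day-57 PR is legitimate. This objection stands for bone. It does not touch the clinical-progression case.

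A reader might also infer more than the documents support:

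- *That a same-date SD makes a responder.* It does not. ORR counts CR and PR only.
- *That such a patient has a one-day duration of response.* SAP 8.7.4.1 limits DoR to confirmed responses. A first PR on the PD date has no later admissible result to confirm it, so entry into DoR is not established.
- *That the clinical benefit rate is inflated.* That rate is undefined and appears only in the PSA text of SAP 8.7.3.1. Nothing shows that soft-tissue SD feeds it.
- *That the type I error doubles or triples.* The two-stage rejection probability does rise from 2.2% to 4.3% or 7.4% if the apparent rate moves from 5% to 6% or 7%. Those shifts are assumed, because no discordance rate is given. SAP 8.7.6 records that enrollment in both mCRPC arms was stopped after the August 2022 interim, so the 33-patient test is no longer the operative one.

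**Conclusion.** The derivation is wrong as written. A first soft-tissue CR or PR that shares its date with bone or clinical progression is counted as a response in the primary ORR, and no other section of the protocol or SAP gives PD precedence on that date. A same-date SD displaces PD in the BOR table only.

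The effect per patient is 3.0 points at n = 33 and 5.0 points at n = 20. The final number of evaluable patients per arm is not stated, so these denominators are the planned ones. The number of affected patients is unknown and may be zero. For bone, the conclusion also assumes that progression is dated at the scan that first shows it. What is affected is the final mCRPC ORR, its confidence interval and the BOR table. SAP Version 2.0 (April 2023) still describes that final analysis as to come, and the trial is open-label, so the rule should be written down rather than left to programming.

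**What to change.** Add to the PCWG3 BOR definition in SAP 8.2:

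1. If any PD component falls on the same date as a CR, PR or SD component, or at the same scheduled imaging assessment in the case of CT/MRI and bone scan, the overall PCWG3 response at that assessment is PD.
2. Only CR, PR or SD from assessments before the first PD assessment count towards BOR.
3. Bone progression is dated at the first or at the confirmatory scan, whichever the team chooses. The choice must be stated.

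A wider merge of PSA with imaging inside a visit window is not needed. PSA is not scheduled at C3D15 or C8D15, so such a merge would require a new window. Under item 1, a PSA progression that meets the SAP's rules would override a radiographic response only when the dates are the same. That follows from the SAP's existing definition of PD.

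The cost is a few lines of text and one derivation step, with no new data. ORR and the SD count may fall slightly.

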8.3 Missing Data

All reasonable efforts will be made to obtain complete data for all patients. However, missing observations may occur due to patients lost to follow-up or to noncompliance with required trial visits and / or assessments. Missing data will not be imputed and data analysis will be performed based on the observed values, unless otherwise specified.

8.4 Visit Windows

Every attempt should be made to perform evaluations at the designated time point / visit. Visit windows for visits per cycles, for Safety FU visits, and for Efficacy FU visits are defined in the SoA (see Section 13.6). All visits will be summarized according to the nominal visit.

8.5 Patient disposition

Patient disposition will be summarized by presenting the number and percentage of patients screened, re-screened, number of screening failures, along with a summary of the primary reason for screening failure for the screened set.

The number and percentage of patients eligible to participate in the trial, number of randomized patients (for Part 2), and the number and percentage of patients in each analysis set will be summarized by treatment group for the patients in the screened set.

For each analysis set (e.g., ITT set, mITT set, Safety set, PP set and Pharmacodynamic set) the number and percentage of patients being excluded from the analysis set will be presented by treatment group along with a summary of the reasons for exclusion based on

the ITT set. In addition, the number of patients in the subsequent cemiplimab monotherapy on progression set will be reported.

The number and percentage of screened / randomized / treated patients will be presented by country and site including the number and percentage of patients with important protocol deviations (by treatment group) for the screened set.

For the ITT set the treatment status will be reported, including the number and percentage of patients having prematurely discontinued treatment by treatment group along with a summary of the primary reason for premature treatment discontinuation of W_pro1 treatment, of cemiplimab treatment and of ADT treatment (e.g., completed per protocol, AEs, disease progression, death, withdrawal of consent, lost to follow-up), as applicable.

Further, the number and percentage of patients started follow-up period, and end of trial disposition will be reported including the number and percentage of patients having completed or discontinued the trial with a summary of the primary reason for trial discontinuation including the number of deaths.

Important protocol deviations will be summarized for the ITT set by treatment group. In addition, a table will be generated summarizing the number and percentage of patients with a protocol deviation due to COVID-19 for the ITT set.

All data will be listed (patient disposition listing, protocol deviation listing, protocol deviation due to COVID-19 listing), and a listing of all patients excluded from any of the analysis sets including the primary reason for exclusion from the analysis sets.

In addition, a listing of all inclusion and exclusion criteria which were not met, based on the screened set will be generated.

Further, the following listings will be generated for the ITT set to report the impact of COVID-19 to patients enrolled in this trial:

- Patients impacted by COVID-19 related trial disruption
- Missing Visits due to COVID-19

8.6 Baseline characteristics

8.6.1 Demographics

Demographic and baseline variables will be summarized for patients in the mITT set. Age (years), weight (kg), height (cm), body mass index (kg/m²) and Glomerular filtration rate (mL/min/1.73 m²) will be summarized as continuous data. Age (< 50 years, >= 50 - <65 years, >= 65 years), Gender (must be male), Ethnicity (Hispanic or Latino, Not Hispanic or Latino, Not Reportable), race (White, Black or African American, Asian, American Indian or Alaska Native, Native Hawaiian or Other Pacific Islander, Not Reportable, Unknown, Other) and BMI categories (<18 kg/m², >=18 kg/m² - <25 kg/m², >=25 kg/m² - <30 kg/m², >=30 kg/m²) will be summarized as categorical data.

Demographic tables for the ITT set, Safety set and the PP set will be generated, depending on the number of patients excluded from the respective analysis set.

A listing of demography will be provided for the ITT set.

8.6.2 Disease characteristics

Disease characteristics will be summarized for patients in the mITT set. Time from initial diagnosis to enrollment will be summarized as continuous data. Tumor stage at diagnosis, tumor grade (Gleason Score) at diagnosis, National Comprehensive Cancer Network (NCCN) Risk Group at diagnosis, PSA level at diagnosis (ng/mL), prostate cancer diagnosis at screening (mCRPC, LPC), tumor stage at screening, ECOG performance status at baseline, tetanus vaccination status, histology will be summarized as categorical data.

Further, on the basis of the initial tumor response assessment (based on PCWG3) reported at the Screening visit, the following variables will be reported:

- Disease Characteristics – Imaging: Target Lesions (Absent / Present), Non-Target Lesions (Absent / Present), Locations of Target Lesions (Anus, Abdominal Cavity, Other - as collected in the database) and Sum of target lesion diameters.

Further information regarding bone lesions at screening to be reported:

Bone-only disease (patients with no target and no non-target lesion at screening evaluation, only bone lesions reported), Bone lesions (Yes, No), in case of “Yes” the total number of lesions related to metastatic disease (1, 2-4, 5-9, 10-20, >20).

Visceral metastasis (Yes, No) defined based on the location of target or non-target lesions at screening evaluation. For more details see Section [13.5](#).

Further the number of patients with at least one visceral metastasis (target or non-target lesions) in liver and lung separately, will be reported.

Lymph node metastasis (Yes, No) defined based on the location of target or non-target lesions at screening evaluation with location = Lymph Node.

Disease characteristics data will be listed for the ITT set.

8.6.3 Prior anti-cancer treatments

The following prior anti-cancer therapies will be summarized using frequency tables for the mITT set.

- Prior cancer surgery
- Prior cancer radiotherapy
- Prior systemic cancer therapy

Prior cancer surgeries will be coded using Medical Dictionary for Regulatory Activities (MedDRA version 22.1 or later version).

Prior systemic cancer therapies will be coded using the World Health Organization Drug Dictionary (WHO-DD) drug codes of the most recent version (WHO-DD Global B3 Sep

2019, or later version) resulting in Anatomical-Therapeutic-Chemical (ATC) codes indicating therapeutic classification.

The number and percentages of patients with any prior cancer surgery will be summarized by System Organ Class (SOC) and Preferred Term (PT) for each treatment group.

All prior cancer therapy types as specified below:

A table "Prior Therapy Lines" will be generated including:

- Number of prior systemic cancer therapies per patient, setting of last systemic cancer therapy (adjuvant, neoadjuvant, palliative, other, unknown), disease status at the end of the last prior systemic cancer therapy (CR, PR, PD, SD, NE, Unknown, Non-Progressive disease), Reasons for termination of the last prior systemic cancer therapy (AE, Disease Progression, Other, Unknown, Completion of therapy)

A table "Prior Therapy Types" will be generated including the number of patients and percentages of

- Any prior cancer surgery including information of treatment intent (palliative, curative, diagnostic, unknown)
- Any prior cancer radiotherapy including information of site and setting (adjuvant, neoadjuvant, palliative, curative, unknown)
- Any prior systemic cancer therapy including information of setting (adjuvant, neoadjuvant, palliative, other, unknown)
- Number of patients with any prior systemic cancer therapy with Docetaxel or other Taxanes. (Use ATC Level 4 Code = L01CD (Taxanes) for the derivation)
- Number of patients with any prior systemic cancer therapy with ADT or Degarelix. (Use ATC Level 4 Code = L02AE (Gonadotropin releasing hormone analogues), to identify all ADTs, L02BX (Other hormone antagonists and related agents) and standardized medication name = Degarelix or Degarelix acetate for the selection of Degarelix.) Including details of Adjuvant or Neo-adjuvant ADT or Degarelix therapy
- Number of patients with any prior systemic cancer therapy: Novel hormone therapies (Use ATC Level 4 Code = L02BB (Anti-Androgens) and L02BX (Other hormone antagonists and related agents), except medication name = Degarelix or Degarelix acetate)

Prior cancer surgery, prior cancer radiotherapy and prior systemic cancer therapy will be listed for the ITT set.

